3.1. Criteria for eliminating data from Analysis Sets

Elimination codes will be used to identify participants to be eliminated from analysis. Details are provided below for the Enrolled Set, the Exposed Set (ES) and the Per Protocol Set (PPS).

3.1.1. Elimination from Enrolled Set

The following codes will be used for identifying participants to be eliminated from the Enrolled Set:

- Code 800 (Fraudulent data)
- Code 900 (Invalid informed consent)

^[2] Contribution of participants to PPS will be defined by timepoint.

3.1.2. Elimination from ES

The following codes will be used for identifying participants to be eliminated from the ES:

- Code 800 (Fraudulent data)
- Code 900 (Invalid informed consent)
- Code 1030 (Study intervention not administered at all)

3.1.3. Elimination from PPS

A participant will be excluded from the populations for analysis under the following conditions:

- For codes 800, 900, 1030 and 1050: participants will be eliminated for all visits.
- For codes 1040, 2010, 2040 and 2050: participants will be eliminated from a specific visit (at which the condition is met) onwards.
- For codes 1070, 1080, 1090: participants will be eliminated from a specific visit (at which the condition is met) onwards for the specific group/antigens in the control group and for both RSV PPS & mRNA COVID-19 PPS in the Co-ad group.
- For codes 2020, 2090, 2100, 2120: participants will be eliminated at the specific visit at which the condition is met for the specific group/antigens.
- For code 2080: participants in the control group will be eliminated from the specific visit at which the condition is met onwards for the RSV PPS.

Table 2 List of elimination codes

Code	Condition under which the code is used	Visit / Contact (timepoints) where the code is checked	Applicable for analysis set/endpoint
800	Fraudulent data	All	Enrolled Set, ES, RSV PPS, COVID-19 mRNA PPS
900	Invalid informed consent	All	Enrolled Set, ES, RSV PPS, COVID-19 mRNA PPS
1030	Study intervention not administered at all	All	ES, RSV PPS, COVID-19 mRNA PPS
1040	Administration of concomitant vaccine(s) forbidden in the protocol: Use of any investigational or non-registered vaccine other than the study intervention during the period beginning 30 days before the dose of study intervention, or planned use during the study period.	All	RSV PPS, COVID-19 mRNA PPS

Code	Condition under which the code is used	Visit / Contact (timepoints) where the code is checked	Applicable for analysis set/endpoint
	 Planned or actual administration of a vaccine not foreseen by the study protocol in the period starting 30 days before and ending 30 days after the dose of study intervention administration (1), with the exception of inactivated and subunit influenza vaccines which can be administered up to 14 days before or from 14 days after the study vaccination. Administration of any SARS-CoV-2 vaccine during the 3 months preceding the study COVID-19 mRNA vaccine administration Previous vaccination with licensed or investigational RSV vaccine. 		•
1050	Randomization failure: participant not randomized in the correct stratum	Visit 1	RSV PPS, COVID-19 mRNA PPS
1070	Vaccine administration not according to protocol: Participant was vaccinated with the correct vaccine but containing a lower volume. Wrong replacement or study vaccine administered (not compatible with the vaccine regimen associated to the treatment number) Route of the study vaccine is not intramuscular. Side of administration wrong (only applicable for Co-ad group if both vaccines are given in the same arm) Wrong reconstitution of administered vaccine	Visit 1 for Co-ad. Visit 1 & 2 for control group.	RSV PPS, COVID-19 mRNA PPS
1080	Vaccine administration after a temperature deviation Vaccine administered despite a Good Manufacturing Practices (GMP) no-go temperature deviation	Visit 1 for Co-ad. Visit 1 & 2 for control group.	RSV PPS, COVID-19 mRNA PPS
1090	Vaccine administration after expiration	Visit 1 for Co-ad. Visit 1 & 2 for control group.	RSV PPS, COVID-19 mRNA PPS
2010	Protocol deviation linked to inclusion/exclusion criteria	Visit 1 & 2 for Co-ad. Visit 1, 2 & 3 for control group.	RSV PPS, COVID-19 mRNA PPS
2020	Pre-dose results are missing	Visit 1 for Co-ad. Visit 1 & 2 for control group.	RSV PPS, COVID-19 mRNA PPS
2040	 Administration of any medication forbidden by the protocol Use of any investigational or non-registered product (drug or invasive medical device (2)) other than the study intervention during the period beginning 30 days before the dose of study intervention, or planned use during the study period. Chronic administration of immune-modifying drugs (defined as more than 14 consecutive days in total) and/or planned use of long-acting immune-modifying treatments at any time up to the last blood sampling visit. Up to 3 months prior to the study intervention administration: 	Visit 1 & 2 for Co-ad. Visit 1, 2 & 3 for control group.	RSV PPS, COVID-19 mRNA PPS

Code	Condition under which the code is used	Visit / Contact (timepoints) where the code is checked	Applicable for analysis set/endpoint
	 For corticosteroids, this will mean prednisone ≥20 mg/day, or equivalent. Inhaled and topical steroids are allowed. Administration of immunoglobulins and/or any blood products or plasma derivatives. Up to 6 months prior to study intervention administration: Long-acting immune modifying drugs including among others immunotherapy (e.g., TNF-inhibitors), monoclonal antibodies, antitumoral medication. 		
2050	Intercurrent medical condition: Participants may be eliminated from the PPS for immunogenicity if, during the study, they incur a condition that has the capability of altering their immune response or are confirmed to have an alteration of their initial immune status.	Visit 1 & 2 for Co-ad. Visit 1, 2 & 3 for control group.	RSV PPS, COVID-19 mRNA PPS
2080	Participants did not comply with vaccination schedule for the control group.	Visit 2 for control group	RSV PPS for control group
	 Number of days between COVID-19 mRNA vaccine and RSV vaccine is outside [30-42 days] 		
2090	Participants did not comply with blood sample schedule: For Co-ad and control group: Number of days between vaccination (Visit 1) and blood sample (Visit 2) is outside [30-42] days. For control group: Number of days between vaccination (Visit 2) and blood sample (Visit 3) is outside [30-42] days.	Visit 2, Visit 3	RSV PPS, COVID-19 mRNA PPS
2100	Immunological results not available post-vaccination	Visit 2, Visit 3	RSV PPS, COVID-19 mRNA PPS
2120	Obvious incoherence/abnormality or error in laboratory data Unreliable released data as a result of confirmed sample mismatch or confirmed inappropriate sample handling at laboratory.	Visit 1 & 2 for Co-ad. Visit 1, 2 & 3 for control group.	RSV PPS, COVID-19 mRNA PPS

⁽¹⁾ In case an emergency mass vaccination for an unforeseen public health threat (e.g.: a pandemic) is recommended a1d/or organized by the public health authorities, outside the routine immunization program, the time period described above can be reduced if necessary for that vaccine provided it is used according to the local governmental recommendations and that the Sponsor is notified accordingly.

⁽²⁾ EEC directive 93/42/EEC defines an invasive medical device as 'A device which, in whole or in part, penetrates inside the body, either through a body orifice or through the surface of the body'.

4. STATISTICAL ANALYSES

4.1. General Considerations

4.1.1. General Methodology

- For the purpose of immunogenicity analyses, any missing or non-evaluable immunogenicity measurement will not be replaced. The descriptive analysis performed for each assay at each time point will exclude participants with a missing or non-evaluable measurement.
- Titers/concentrations below the assay cut-off (LLOQ) will be replaced by half the assay cut-off (LLOQ/2) and titers/concentrations above the upper limit of quantification (ULOQ) will be replaced by the ULOQ to compute GMTs/GMCs, SRRs and MGIs. For the display of reverse cumulative curve, titers/concentrations below LLOQ will be replaced by half the assay cut-off (LLOQ/2) and titers/concentrations above ULOQ will not be replaced.
- Confidence intervals (CIs) will use 95% confidence levels unless otherwise specified (e.g., primary endpoints analysis, refer to Section 4.2.2). 95% CIs for GMT/GMC and MGI will be based on a back transformation of CI for the mean of log₁₀-transformed values. Exact 95% CIs around proportions are derived using the method of Clopper and Pearson [Clopper, 1934]. 95% CI for group difference in proportion will be based on Miettinen and Nurminen confidence interval [Miettinen, 1985].
- Unless otherwise specified, continuous data will be summarized using descriptive statistics: n, mean, standard deviation, median, minimum, and maximum. Categorical data will be summarized as the number and percentage of participants in each category.
- Analysis based on ES and PPS will be performed based on the actual stratum per data collected in the eCRF.

4.1.2. Baseline Definition

For all endpoints the baseline value will be the latest pre-dose assessment with a non-missing value, including those from unscheduled visits. If time is not collected, Day 1 assessments are assumed to be taken prior to first dose and used as baseline.

Unless otherwise stated, if baseline data is missing no derivation will be performed and baseline will be set to missing.

4.2. Primary Endpoint(s) Analyses

The primary analysis set will be the PPS. If, in any group, the percentage of vaccinated participants with serological results excluded from the PPS is more than 5%, a second analysis based on the ES will be performed to complement the PPS analysis.

4.2.1. Definition of endpoints

- RSV-A and RSV-B neutralizing titers measured at 1 month (at Day 61 for Control group, at Day 31 for Co-ad group) after RSVPreF3 OA investigational vaccine administration) expressed as GMT ratio with 95% CIs between Control group versus Co-ad group.
- SARS-CoV-2 Omicron XBB.1.5 neutralization titers measured at 1 month (at Day 31 for both groups) after COVID-19 mRNA vaccine administration expressed as GMT ratio with 95% CIs between Control group versus Co-ad group.

4.2.2. Main analytical approach

Considering the sampling timepoint at 1-month post-study intervention administration:

The least square point estimate and the 2-sided 95% CI for group GMT ratio between RSVPreF3 OA investigational vaccine administered alone (Control group) over RSVPreF3 OA investigational vaccine when co-administered with the COVID-19 mRNA vaccine (Co-Ad group) will be derived from an analysis of covariance (ANCOVA) model on log10 transformed titer for each neutralization assay. The model will include the treatment group, the age category (age at vaccination: 50-59, 60-69 or ≥70 years) as fixed effects, and the pre-dose log10-transformed titer as covariate.

The group GMT ratios will be based on a back transformation of group contrast in the ANCOVA model applied to the logarithmically transformed titers. Missing data will not be replaced.

Titers below the assay lower limit of quantification (LLOQ) will be replaced by half the assay cut-off, titers above the upper limit of quantification (ULOQ) will be replaced by the ULOQ.

Success criteria for non-inferiority:

The upper limit of the 2 sided 95% CI of the GMT ratio between the Control group (at Day 61) versus Co-ad group (at Day 31) for RSV-A neutralization titer 1-month after the RSVPreF3 OA investigational vaccine dose is ≤ 1.5 .

AND

The upper limit of the 2-sided 95% CI of the GMT ratio between the Control group (at Day 61) versus Co-ad group (at Day 31) for RSV-B neutralization titer 1-month after the RSVPreF3 OA investigational vaccine dose is \leq 1.5.

AND

The upper limit of the 2 sided 95% CI of the GMT ratio between the Control group (at Day 61) versus Co-ad group (at Day 31) for SARS-CoV-2 neutralization titer 1-month after the COVID-19 mRNA vaccine dose is <1.5.

The results will be presented in tables as well as graphs using forest plots.

Results for RSV-A & RSV-B will be reported using ED60.

4.3. Secondary Endpoint(s) Analyses

4.3.1. Immunogenicity analysis

The analysis will be based on the PPS. If, in any group, the percentage of vaccinated participants with serological results excluded from the PPS is more than 5%, a second analysis based on the ES will be performed to complement the PPS analysis.

4.3.1.1. Definition of endpoints

- RSV-A and RSV-B neutralizing titers measured at 1 month (at Day 61 for Control group, at Day 31 for Co-ad group) after RSVPreF3 OA investigational vaccine administration) expressed as GMC ratio with 95% CIs between Control group versus Co-ad group.
- RSV-A and RSV-B neutralizing titers measured at pre-vaccination (at Day 1 for Coad group and at Day 31 for Control group) and at 1 month (at Day 31 for Co-ad group and at Day 61 for Control group) after RSVPreF3 OA investigational vaccine administration expressed as GMTs/GMCs with 95% CIs.
- Fold increase in RSV-A and RSV-B neutralizing titers from pre-vaccination to 1-Month post RSVPreF3-OA investigational vaccine administration expressed as MGIs with 95% CIs.
- RSV-A and RSV-B neutralizing titers ≥ assay cut-off at pre-vaccination and 1 month after the RSVPreF3 OA investigational vaccine dose administration expressed as percentage of participants having RSV-A and RSV-B neutralizing titers/concentrations ≥ cut-off with 95% CIs.
- Seroresponse rate in RSV-A and RSV-B, defined as a fold increase in neutralizing titers from pre-vaccination to 1-Month post RSVPreF3-OA investigational vaccine administration ≥4 expressed as SRR with 95%CIs.
- SARS-CoV-2 Omicron XBB.1.5 neutralization titers measured at pre-vaccination (at Day 1) and at 1 month (at Day 31) after COVID-19 mRNA vaccine administration expressed as GMTs with 95% CIs.
- Fold increase in SARS-CoV-2 Omicron XBB.1.5 neutralization titers from prevaccination to 1-Month post COVID-19 mRNA vaccine administration expressed as MGIs with 95% CIs.
- SARS-CoV-2 Omicron XBB.1.5 neutralizing titers ≥ assay cut-off at pre-vaccination and 1 month after the COVID-19 mRNA vaccine dose administration expressed as percentage of participants having SARS-CoV-2 Omicron XBB.1.5 neutralizing titers ≥ cut-off with 95% CIs.

4.3.1.2. Main analytical approach

For each study group, each immunological assay and at each time point that blood samples are collected, the following analysis will be performed:

- Considering the sampling timepoint at 1-month post-study intervention administration, same analysis as for RSV-A/RSV_B primary endpoint (refer to Section 4.2.2) will be performed using IU/ml unit for computation of the GMC ratio.
- Percentage of participants with neutralizing titers/concentrations equal to or above pre-defined assay cut-offs and their 2-sided 95% CIs will be tabulated.
- Percentage of participants having a fold increase in RSV-A & RSV-B neutralizing titers/concentrations ≥4 and their 2-sided 95% CIs will be tabulated.
- Unadjusted GMTs/GMCs and their 95% CIs will be tabulated and displayed graphically.
- Unadjusted MGIs and their 95% CIs will be tabulated.
- Results for RSV-A & RSV-B will be reported using both ED60 and IU/ml units.
- Distribution of neutralizing titers/concentrations will be displayed using reverse cumulative curves.

4.4. Safety Analyses

The safety analyses will be based on the ES.

4.4.1. Adverse Events

An adverse event (AE) is considered study intervention emergent if the AE onset date is on or after study intervention start date. All AE summaries will be based on study intervention emergent events unless otherwise specified. SAE summaries will be based on all SAEs reported regardless of whether they meet the definition of study intervention emergent or not. All AE and SAE summaries will be grouped by SOC, HLT and PT and summarized by study intervention group at time of onset of the AE, unless otherwise specified.

Adverse events will be coded using the standard Medical Dictionary for Regulatory Activity (MedDRA dictionary). The verbatim reports of unsolicited AEs, including SAE and AESI, will be reviewed by a qualified person and the signs and symptoms will be coded according to the MedDRA Dictionary for Adverse Reaction Terminology. Every verbatim term will be matched with the appropriate Preferred Term.

For the summaries of AE and SAE, participants who experience the same AE/SAE (in terms of the MedDRA SOC, HLT and PT) more than once will only be counted once for that event in the number of participants but all occurrences of the same event will be counted in the number of events. Also, in the case of co-administered study interventions, an administration site event recorded for a participant following multiple study interventions will be counted as only one occurrence.

A study intervention-related AE/SAE is defined as an AE/SAE for which the investigator classifies the possible relationship to study intervention as "Yes". A worst-case scenario approach will be taken to handle missing relatedness data, i.e., the summary table will include events with the relationship to study intervention as 'Yes' or missing.

The analyses of unsolicited AEs will include SAEs and AESIs (unless otherwise specified).

The following analysis will be performed:

- Compliance in completing solicited events information will be tabulated after each dose and overall.
- The number and percentage of participants with at least one administration site event (solicited and unsolicited), with at least one systemic event (solicited and unsolicited) and with any AE (solicited and unsolicited) during the 4-day or 30-day follow-up period after vaccination will be tabulated with exact 95% CI for each group, after each dose and overall.
- The same computations will be done for Grade 3 AEs, for Grade 3 non-serious AEs and for AEs resulting in a medically attended visit.
 - Those analyses will present all solicited and unsolicited AEs, including SAEs and AESIs (unless otherwise specified).
- The number and percentage of participants with at least one administration site event (solicited only), with at least one systemic event (solicited only) and with any solicited event during the 4-day follow-up period after vaccination will be tabulated with exact 95% CI for each group, after each dose and overall.
- The same computations will be done for Grade 3 AEs and for AEs resulting in a medically attended visit.
- The number and percentage of participants reporting each individual solicited administration site or systemic event (any grade, Grade 3 and resulting in medically attended visit) during the 4-day follow-up period after vaccination will be tabulated with exact 95% CI for each group, after each dose and overall.
- For fever, the number and percentage of participants reporting fever by half degree (°C) cumulative increments during the 4-day follow-up period after vaccination will be tabulated for each group, after each dose and overall.
- The percentage of participants with each solicited administration site event and solicited systemic event (any grade and Grade 3) during the 4-day follow-up period after vaccination will be represented graphically for each group after each dose and overall.
- The duration in days of each individual solicited events will be tabulated using descriptive statistics (mean, min, Q1, median, Q3, maximum).
- The number of days with Grade 3 solicited events will be tabulated for each individual solicited event using descriptive statistics (mean, min, Q1, median, Q3, maximum).

- The number and percentage of participants with any unsolicited AEs during the 30-day follow-up period (i.e., the day of vaccination and 29 subsequent days) with its exact 95% CI will be tabulated by group and by Medical Dictionary for Regulatory Activities (MedDRA) Primary System Organ Class (SOC), High Level Term (HLT) and Preferred Term (PT), after each dose and overall. Similar tabulation will be done for Grade 3 unsolicited AEs, for any causally related unsolicited AEs, for Grade 3 causally related unsolicited AEs and for unsolicited AEs resulting in a medically attended visit.
- The number and percentage of participants with any non-serious unsolicited AEs during the 30-day follow-up period with its exact 95% CI will be tabulated by group and by MedDRA Primary System Organ Class (SOC), High Level Term (HLT) and Preferred Term (PT), after each dose and overall. Similar tabulation will be done for Grade 3 non-serious unsolicited AEs, for any causally related non-serious unsolicited AEs and for non-serious unsolicited AEs resulting in a medically attended visit.
- The number and percentage of participants with any unsolicited AEs reported within 30 minutes following vaccination with its exact 95% CI will be tabulated by group and by MedDRA Primary System Organ Class (SOC), High Level Term (HLT) and Preferred Term (PT), after each dose and overall. Similar tabulation will be done for Grade 3 unsolicited AEs reported within 30 minutes following vaccination.
- The number and percentage of participants with at least one report of SAE classified by the MedDRA Primary SOC, HLT and PT from vaccination up to study end (i.e., 6 months after last vaccination) will be tabulated with exact 95% CI.
- The same tabulation will be presented for causally related SAE, fatal SAE, pIMD and causally related pIMD.
- All SAEs/AESIs up to study end (i.e., 6 months after last vaccination) will also be described in detail in a tabular listing.
- AEs/SAEs leading to study discontinuation from vaccination up to study end will be tabulated.
- For web posting purposes, the number of occurrences and the number and percentage of participants with non-serious AEs (solicited and unsolicited combined) during the 30-day follow-up period (i.e., the day of vaccination and 29 subsequent days) will be produced by SOC and PT.
- In case of pregnancies, these will be described in detail.

For analysis of SAEs/AESIs within 6 months, the reporting period will start at vaccination and will end at Day 183 after each dose, computed as 6 x 30.5 days = 183 days.

Refer to Section 6.1.4 and Section 6.1.5 for the analysis of concomitant medications and concomitant vaccination.

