1.3. Schedule of activities (SoA)

Table 1 SoA for Co-Ad group

Type of contact	Visit 1	Visit 2**	Contact	N-4				
Timepoints	Day 1	Day 31	Month 6 ¹	Notes				
Baseline and demography assessments								
Informed consent	•2			See Section 10.1.3				
Distribution of participant card	0			See Section 8.4.8				
				See Section 5.1 and Section				
Inclusion and exclusion criteria	•			5.2 for Inclusion and Exclusion				
				criteria				
Check with participant if he/she will appoint a								
caregiver and distribute caregiver information	0	0		See Sections 8 for details				
letter, when applicable								
Demography	•			See Section 8.1.1				
Medical and vaccination history	•			See Sections 8.1.2				
History directed physical examination	0			See Section 8.3.1				
Screening conclusion	•			See Section 5.4				
Laboratory assessment								
Urine pregnancy test (only for women of	•3			See Section 8.3.3				
childbearing potential)				occ occilon 6.5.5				
Blood sampling from all participants for	•4	● 5		See Section 8.2.2				
humoral response assessment (~15 mL)				000 00011011 0.2.2				
Study Intervention administration			11					
Check contraindications, warnings and	0			See Sections 7.1.1				
precautions to vaccination								
Check criteria for temporary delay for								
enrollment and/or study intervention	0			See Section 5.5				
administration*								
Randomization, study group and intervention	0			See Section 6.3.2 and Section				
number allocation				6.3.3				
				The preferred location for				
				measuring temperature will be				
Body temperature before study interventions	_			oral cavity/axilla (see Section 8.1.3). Fever is defined as				
administration	•			temperature ≥38.0°C/100.4°F,				
				regardless of the location of				
				measurement.				
Study interventions administration (COVID-19				meddarement.				
mRNA vaccine + RSVPreF3 OA								
investigational vaccine on separate arms)	•			See Section 6.1				
(including 30-minute post-vaccination								
observation)								
Recording of administered study interventions				0 0 11 000				
numbers	•			See Section 6.3.3				
Safety assessment								
Distribution of diary cards for solicited events				0 04 40.3.5				
and unsolicited AEs	0			See Section 10.3.5				
Record concomitant medications/vaccinations	•	•	•	See Section 6.9				
Recording of intercurrent medical conditions	•	•	•	See Section 9.2.1 and Table 9				
Recording of solicited events (Days 1–4 after	_							

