4. STUDY DESIGN

4.1. Overall design

The study design overview is presented in Figure 1.

- Type of study: Self-contained.
- **Experimental design:** Phase 3, randomized, open-label study with 2 parallel groups (see Figure 1).
- **Study groups and randomization:** Approximately 830 eligible participants will be randomly assigned (1:1) to the following 2 groups: Co-Ad group and Control group at Visit 1 (Day 1). Each group will include approximately include 415 participants.

• Vaccination schedule:

- Co-Ad group: Participants will receive a single dose of COVID-19 mRNA vaccine and a single dose of RSVPreF3 OA investigational vaccine at Visit 1 (Day 1).
- Control group: Participants will receive a single dose of COVID-19 mRNA vaccine at Visit 1 (Day 1), followed by a single dose of the RSVPreF3 OA investigational vaccine at Visit 2 (Day 31).
- **Primary completion date:** Day 61 (1 month after the RSVPreF3 OA investigational vaccine dose in Control group).
- **Duration of the study:** ~ 6 months for participants in Co-Ad group; ~ 7 months for participants in Control group.
- **Control:** Active comparator, i.e., staggered administration of licensed COVID-19 mRNA vaccine and RSVPreF3 OA investigational vaccine.
- **Blinding:** Open-label. Refer to Section 6.4 for details.
- **Data collection:** Standardized eCRF. Solicited events and unsolicited AEs will be collected using a participant Diary card (paper Diary card).
- **Safety monitoring:** The study will be conducted with oversight by the project SRT. Please refer to Section 10.1.6 for the SRT structure.

• Enrollment rules:

Overall, participants will be enrolled in 3 age categories reflecting an approximate age distribution in the general population with a balance between males and females. It is therefore intended to enroll:

• Approximately 30% of participants 50-59 YOA, approximately 30% of participants 60-69 YOA and approximately 25% of participants ≥ 70 YOA. The remaining 15% can be distributed freely across the 3 age categories. The enrollment of participants as per the age categories, and percentage of participants in each age category, if any, will be guided by the feasibility assessment.

• Approximately 40% of participants from each sex; the remaining 20% can be distributed freely between the two sexes.

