6.1. Study interventions administered

Refer Section 4 for the study intervention administration schedule.

Table 5 Study Intervention(s) Administered

Study intervention name:	RSVPreF3 OA inv	estigational vaccine	Comirnaty Omicron XBB.1.5 COVID-19 mRNA vaccine
Study intervention formulation:	RSVPreF3 (120 µg)	AS01 _E : QS-21* (25 μg), MPL (25 μg), liposomes; Water for injections	Raxtozinameran (30 µg) embedded in LNP; Water for injections
Presentation:	Powder for suspension for injection; in vial	Suspension for suspension for injection; in vial	Dispersion for injection; in vial
Туре:	Inv	restigational	Comparator
Product category:		Biological	Biological
Route of	l II	M injection	IM injection
administration:			
Administration site:			
 Location 	Deltoid		Deltoid
 Directionality 	Upper		Upper
 Laterality ** 	Co-ad group: Dominant		Co-ad group: Non-dominant
•	Control gr	oup: Non-dominant	Control group: Non-dominant
Number of doses to be administered:		1	1
Volume to be	0.5 mL		0.3 mL
administered by dose ***			
Packaging and	Refer to the ph	armacy manual for more	Refer to the pharmacy
labelling:		details	manual for more details
Manufacturer:	GSK	Biologicals SA	Pfizer-BioNTech

IM: Intramuscular; LNP: Lipid nanoparticle; MPL: Monophosphoryl lipid A.

217848 (RSV OA=ADJ-013) Protocol Final

Study participants must be observed closely for at least 30 minutes after the administration of the study interventions. Appropriate medical treatment must be readily available during the observation period in case of anaphylaxis, syncope.

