To evaluate the safety and reactogenicity following administration of the RSVPreF3 OA investigational vaccine and a COVID-19 mRNA vaccine, co-administered or administered alone.	 Percentage of participants reporting each solicited administration site event and systemic event within 4 days post study intervention administration (i.e., the day of vaccination and 3 subsequent days). Percentage of participants reporting unsolicited AEs within 30 days post study intervention administration (i.e., the day of vaccination and 29 subsequent days). Percentage of participants reporting SAEs after study intervention administration (Day 1) up to study end (6 months after last study intervention administration). Percentage of participants reporting pIMDs after study intervention administration (Day 1) up to study end (6 months after last study intervention administration).

AE: adverse event; GMT: Geometric Mean Titer; MGI: Mean Geometric Increase; pIMD: potential immune mediated disease; SAE: serious adverse event, SRR: Seroreponse rate. MGI and SRR are defined in Section 4.1.1

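### Co-Ad local reactions are planned only as an any-site figure, so no table shows whether either vaccine's local reactogenicity changes with co-administration

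*SAP*

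**What the plan says.** The secondary safety objective (SAP 1.1) is "To evaluate the safety and reactogenicity following administration of the RSVPreF3 OA investigational vaccine and a COVID-19 mRNA vaccine, co-administered or administered alone". The estimand in SAP 1.1.1.2 summarises each endpoint as a percentage of participants by group.

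Protocol 1.3 (Table 1) has Co-Ad participants receive the COVID-19 mRNA vaccine and the RSV "investigational vaccine on separate arms" at Visit 1. Protocol 6.1, Table 5, gives the planned arm: for the RSV vaccine "Co-ad group: Dominant", for the COVID-19 vaccine "Co-ad group: Non-dominant". In Control both vaccines are planned for the non-dominant arm, about a month apart (Protocol 4.1). A footnote to Table 5 makes the non-dominant arm a preference and allows the other arm when that one cannot be used.

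SAP 4.4.1 states that, for co-administered interventions, "an administration site event recorded for a participant following multiple study interventions will be counted as only one occurrence". On the solicited tables it says: "The number and percentage of participants reporting each individual solicited administration site or systemic event" during the 4-day period "will be tabulated with exact 95% CI for each group, after each dose and overall". The graphs and the age-subgroup tables (SAP 4.5.1.2) use the same breakdown. No table in either document is specified by vaccine or by injection site within Co-Ad.

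**The concern.** The objective sets co-administration against administration alone. Control supplies each vaccine's local reaction rate when given alone: the COVID-19 vaccine after Day 1, the RSV vaccine after Day 31. The Co-Ad counterpart of each rate is the rate at that vaccine's own site, and that figure is not planned.

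Two things are at stake. First, the per-dose displays put a two-injection figure next to one-injection figures. A reader who compares them directly may see more local reactions in Co-Ad even if neither vaccine behaves differently. Second, the overall columns compare like with like for total local burden, but they weaken a change confined to one site and cannot say which vaccine it belongs to.

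The immunogenicity primary endpoints are not affected.

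**Working it through.** The plan states no figure on this point, so there is none to reproduce. The check has two parts: whether any rule separates the two Co-Ad sites, and what a merged rate can reveal.

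**1. Is there a split anywhere?**
- The word dose does not provide one. Protocol 8.2.3 (Table 8) labels the joint Co-Ad administration as dose 1, and Protocol 8.4.1 (Table 9) gives it a single vaccination column.
- SAP 6.3.1 attributes events to a dose. SAP 6.3.5.3 defines the denominator from a yes/no answer about site events as a class. SAP 6.3.6.7 counts events with the same preferred term and start day once. SAP 6.3.6.8 counts each event once per period. None refers to the injection site.

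**2. What the merged rate can be when co-administration changes nothing.** Let pC and pR be the COVID-19-site and RSV-site rates, and u the Co-Ad rate for either site. Then

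max(pC, pR) ≤ u ≤ min(1, pC + pR), and u = pC + pR − pC·pR if the sites are independent.

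The documents give no local reaction rates, so every rate here is an assumption.

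| pC | pR | lowest u | u if independent | highest u |
|---|---|---|---|---|
| 5% | 10% | 10% | 14.5% | 15% |
| 20% | 20% | 20% | 36% | 40% |
| 30% | 50% | 50% | 65% | 80% |
| 40% | 60% | 60% | 76% | 100% |
| 60% | 60% | 60% | 84% | 100% |

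In the last row each Control per-dose rate is 60%. The apparent excess is 60 − 60 = 0 points at the least, 84 − 60 = 24 under independence, and 100 − 60 = 40 at the most.

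**3. Can u reveal a change at one site?** Take rates when given alone of 40% (COVID-19) and 60% (RSV).
- No change, independent sites: overlap 0.40 × 0.60 = 0.24, so u = 0.40 + 0.60 − 0.24 = 0.76.
- RSV site up to 70%, with 34% reacting at both sites: u = 0.40 + 0.70 − 0.34 = 0.76.

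An overlap of 34% is possible, since it cannot exceed 40%. The same 76% fits both no change and a 10-point rise at the RSV site. Only extreme results are informative. If u is no higher than a vaccine's alone rate, an increase for that vaccine is ruled out. If u exceeds the sum of the two alone rates, at least one has risen.

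**4. How far the overall comparison dilutes a one-site change.** Assume independence, 60% per site alone, and an RSV-site rise to 70% in Co-Ad.
- Co-Ad any site: 1 − 0.30 × 0.40 = 88%. Control overall: 1 − 0.40 × 0.40 = 84%. Difference 4 points.
- By site: 70% against 60%. Difference 10 points.

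With all 415 planned participants per group contributing, approximate 95% half-widths for the differences are 1.96 × √[(0.88 × 0.12 + 0.84 × 0.16)/415] = 4.7 points and 1.96 × √[(0.70 × 0.30 + 0.60 × 0.40)/415] = 6.5 points. The 4-point interval includes zero and the 10-point interval does not. The plan specifies no between-group interval for these events; the calculation only shows scale.

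**The case against.** The strongest reply is that the plan does what its estimand asks. The endpoint is a participant-level percentage by group, the objective is descriptive, and a regimen-level reading of co-administered or administered alone is natural. The overall columns supply a fair regimen-level comparison, and nothing in the SAP tells a reader to set Co-Ad against a single Control dose. All of this stands.

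The count-once sentence is also not the root cause. It limits occurrences, whereas the solicited tables report participants: someone with pain in both arms contributes once to an any-site percentage with or without it. Nor does it forbid a by-site row. The gap is that no such row is planned.

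A reader might infer that the tables must show an artificial excess in Co-Ad, of about 24 points at 60% per site. The documents do not support that. They give no rates, and 24 points needs independent sites, although both belong to one person over the same four days. With positive dependence the excess is smaller, and with equal rates and complete overlap it vanishes.

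A reader might also infer that the arm identifies the vaccine automatically. It does not. The arm is a preference, and elimination code 1070 (SAP 3.1.3, Table 2) foresees both vaccines in one arm. That code removes a participant from the per-protocol sets only, so the participant stays in the Exposed Set used for safety.

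Finally, the RSV by-site comparison would set a planned dominant arm in Co-Ad against a planned non-dominant arm in Control, so arm use could explain part of a difference. The diary card is not among the documents, so whether site events are recorded by arm is unknown; the wording of the counting rule suggests they may be.

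**Conclusion.** The point holds as a limit on interpretation. It is not an internal contradiction or an error in the estimand. As specified, the Co-Ad local rate is an any-site rate. It is valid for the by-group estimand and comparable with Control overall, but it does not show whether either vaccine becomes more or less locally reactogenic when co-administered. Beside one Control dose it can mislead by 0 to 40 points when each site's assumed rate is 60% and nothing has changed. The range depends on the assumed rates and on the unknown dependence between sites. The conclusion that no by-vaccine rate can be read from the planned tables, except at the extremes, needs neither assumption. By-site rows are a cheap improvement to a named secondary objective, provided site-level data exist.

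**What to change.** In SAP 4.4.1:

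- Keep the any-site row, apply the count-once rule to that row only, and name Co-Ad against Control overall as its matching comparison.
- For each solicited administration site event (any grade, Grade 3, medically attended), add Co-Ad RSV-site rows beside Control after the RSV dose, and Co-Ad COVID-19-site rows beside Control after the COVID-19 dose, with exact 95% CIs.
- Assign sites by the actual arm of injection recorded. Leave out of the by-site rows anyone given both vaccines in the same arm.
- Footnote that the planned RSV arm differs by group (dominant in Co-Ad, non-dominant in Control), while the planned COVID-19 arm is the same.
- If the diary or eCRF does not record site events by arm, footnote the per-dose displays as two sites against one, and state that by-vaccine local reactogenicity cannot be assessed. The current SAP amendment is dated 24 March 2025, so it may be too late to change the diary.

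The cost is a few table rows and a SAP sentence, with no extra visits or samples. The downsides are longer tables and reliance on site-level recording.
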